Official Title: Bovine Carotid Artery Biologic Graft and Expanded Polytetrafluoroethylene for Permanent Hemodialysis Access

NCT03300024

Document Date: 10/15/2015

JHM IRB - eForm A – Protocol

A Prospective Randomized Study of Bovine Carotid Artery Biologic Graft and Expanded Polytetrafluoroethylene for Permanent Hemodialysis Access

Protocol Version: Version 1 (IRB00069002)

Protocol Date: 10/15/2015

Type of Study: Investigator initiated study. The principal investigator will have sole responsibility for monitoring and oversight of problem/events for this research.

Institution: Johns Hopkins Medical Institutions, Baltimore, MD, USA

1. Abstract

Arteriovenous grafts (AVG) remain reliable substitutes for permanent hemodialysis access in scenarios that preclude the placement of arteriovenous fistulae. There is scarcity of evidence to support the current preference of synthetic conduits over biologic grafts in clinical practice. Advances in the design of AVG's warrant contemporary comparisons between synthetic and biologic AVG options. This is especially important as biologic conduits may confer an advantage by virtue of their inherent similarity to the native human vasculature. We propose a randomized study to compare bovine carotid artery (BCA) biologic grafts and expanded polytetrafluoroethylene grafts (ePTFE) for permanent hemodialysis access.

2. Objectives

The overall goal of this project is to compare the one and two year patency, complication and intervention rates between BCA and standard ePTFE.

Specific Aim 1: To compare functional primary patency between BCA and ePTFE

Hypothesis 1A: Patients receiving BCA grafts will have a higher primary patency rate at 1 and 2 years follow up than those who receive ePTFE grafts.

Specific Aim 2: To compare functional primary assisted patency between BCA and ePTFE

Hypothesis 2A: Patients receiving BCA grafts will have a higher functional primary assisted patency rate at 1 and 2 years follow up than those who receive ePTFE grafts.

Specific Aim 3: To compare functional secondary patency between BCA and ePTFE

Hypothesis 3A: Patients receiving BCA grafts will have a higher functional secondary patency rate at 1 and 2 years follow up than those who receive ePTFE grafts.

Specific Aim 4: To compare complication (pseudoaneurysms, infection and steal syndromes) rates between BCA and ePTFE

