Will also be given a chance to review the informed consent form (ICF). They will have the option of taking the ICF home or having it mailed or emailed to them before making any decisions. No study related procedures would be performed before written informed consent process. All HIPAA privacy regulation applies here and patient rights as well as responsibilities are incorporated in the informed consent process. Consenting patients will be enrolled into the study and prospectively randomized to receive either BCA or standard ePTFE by an independent study coordinator.

Enrollment

Once enrolled, patients will be randomized to one of two groups: one group will receive the BCA graft (experimental) while the other group will receive any standard ePTFE graft (control). Randomization will be done via a computer-generated list of numbers in a 1:1 ratio using the online tool Research Randomizer.

AVG Placement

Patients will undergo surgery as per standard of care and receive the randomized graft in compliance to National Kidney Foundation Kidney Disease Outcomes Quality Initiative (KDOQI) guidelines for AVG creation¹. The grafts will be placed either in the arm (brachial artery-axillary vein) or forearm (brachial artery to cephalic or suitably sized vein) based on anatomic suitability.

Post-Operative Assessment

The patients and their grafts in both treatment arms will be monitored postoperatively per standard stipulated by KDOQI. In the immediate post-operative period, particular attention will be paid to the presence of thrills or bruits within the graft by the examiner(s) as well as neurologic and circulatory function of the ipsilateral hand. At hemodialysis the grafts will be accessed with 15 or 17 gauge needles inserted at any angle between 25-30 degrees (the same method used for a native arterio-venous fistula).

- b. Study duration and number of study visits required of research participants.

Follow-up

- 1) POD# 10-20: Physical examination by the surgeon or PA as per standard of care. Any thrills or bruits as well as any neurological or circulatory abnormalities in function of the ipsilateral hand will be noted by the examiner.

2) POD# 25-45: Physical examination by the surgeon or PA as per standard of care. Any thrills or bruits as well as any neurological or circulatory abnormalities in function of the ipsilateral hand will be noted by the examiner.

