3) Thereafter; dialysis center 3 times weekly: The graft will be monitored for its functionality during dialysis sessions three times weekly by the nephrologists or trained dialysis nurses. Difficulty during dialysis (disruptions in flow pattern or increased bleeding) or the absence of a thrill or bruit will warrant surgical evaluation. If by physical examination the graft is thrombosed, then the patient will immediately be referred for endovascular thrombectomy and revision. If the graft is patent, but problematic, the patient will be referred for an urgent fistulogram and endovascular intervention.

Patients, dialysis and dialysis access centers will be contacted by the fellow or study coordinator **every three months up to two years** to ascertain function of the graft and monitor outcomes of interest.

Note: This time frame for follow up was chosen because:

- a) It will minimize data lost to follow up.
- b) It will maximize the opportunity for detection of infection, malformations or stenoses since most graft abnormalities are apparent by 30 days postoperatively.
- c) The standard of care at the Johns Hopkins surgical department includes a post-op check and visit 5 to 14 days following surgery.
- d) The follow up continues up to 2 years to report the final outcomes at end of the study.

Outcomes

Outcomes will be assessed and documented per standards for reports dealing with arteriovenous hemodialysis access¹³ and defined as follows. Primary patency: Interval from graft placement to any intervention for stenosis with or without complete occlusion (thrombosis). Assisted primary patency: interval from graft placement to the first episode of complete occlusion. Secondary patency: interval from graft placement to graft failure. Functional patency: interval from first time graft is used for hemodialysis to qualifying event as above. Infection will be defined as the presence of erythema or purulent drainage at

the surgical incision and need for intravenous antibiotics or surgical intervention. Steal syndrome will be staged per standard as follows: Stage I: pale/blue and/or cold hand without pain; Stage II: Pain during exercise and/or hemodialysis; Stage III: Rest pain; Stage IV: Ulcers/necrosis/gangrene. Accordingly, surgical intervention will be carried out for patients with stage III or IV steal.

Innovation

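### If the two-year follow-up runs from graft placement, functional patency at 2 years from first dialysis use falls beyond the end of observation

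*Combined protocol and SAP*

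**What the plan says.** **Endpoints.** In Section 2, Aims 1-3 each name a functional patency measure. Hypothesis 2A reads "Patients receiving BCA grafts will have a higher functional primary assisted patency rate at 1 and 2 years follow up", and Hypothesis 3A makes the same claim for functional secondary patency. The list of primary outcomes in that section gives primary, primary assisted and secondary patency at 1 and 2 years, without the word functional.

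**Definitions (4b, Outcomes).** The base measures start at surgery, for example "Assisted primary patency: interval from graft placement to the first episode of complete occlusion". The functional versions start later: "Functional patency: interval from first time graft is used for hemodialysis to qualifying event as above".

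**Follow-up (4b).** The first two visits are in postoperative days: "POD# 10-20: Physical examination by the surgeon or PA as per standard of care" and "POD# 25-45: Physical examination by the surgeon or PA as per standard of care". The third item is "Thereafter; dialysis center 3 times weekly", and contacts with patients and centers then run "every three months up to two years". Note d adds: "The follow up continues up to 2 years to report the final outcomes at end of the study". Neither sentence says when the two years begin.

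**Analysis (7c).** Kaplan-Meier and Cox methods are named. No time origin or censoring rule is given, and no expected time from placement to first use appears anywhere.

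**The concern.** Follow-up and functional patency run on different clocks, and nothing aligns them. If follow-up closes 24 months after placement, a graft first used *d* months after surgery is observed for at most 24 − *d* functional months. Any delay above zero leaves that patient short of 24.

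Two hypotheses name a 2-year functional rate. On this reading the Kaplan-Meier risk set at that time point is empty, and it thins out beforehand at a rate set by how the delays vary. The analyst would then have to leave the estimate undefined, carry the last value forward, or change the time point after seeing the data. Functional time not collected before contacts stop may not be recoverable.

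**Working it through.** **1. The plan's own figures.** Section 7c gives assisted patency at 1 and 2 years of 60.5% and 40.5% (BCA) and 20.8% and 13.8% (ePTFE). The 2-year difference is 40.5 − 13.8 = 26.7 points. The stated 49 per group is reproduced by a two-sided comparison of 60.5% with 30.5% at alpha 0.05 and 80% power, with continuity correction (43 without it). The plan does not state that pair of proportions. The formula has no time origin, so the sample size is not affected by this point.

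**2. Where the two years could start.**
- From placement: maximum functional follow-up is 24 − *d* months. With assumed delays of 2, 4, 6 and 12 weeks this is 23.5, 23.1, 22.6 and 21.2 months.
- From the postoperative day 25-45 visit: contacts end at 24 + 25/30.44 = 24.8 to 24 + 45/30.44 = 25.5 months after placement. Only grafts first used by that visit reach 24 functional months.
- From first use: no shortfall.

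Placement is the best supported. The numbered visits are in postoperative days, and the note justifying the time frame, which contains the two-year limit, argues in days after surgery. Nothing ties follow-up to first use.

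**3. Effect if every patient had the same delay.** Assume a constant hazard in year 2, apply the planning rates on the functional clock, and carry the last estimate forward.

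Monthly hazard: BCA −ln(0.405/0.605)/12 = 0.0334; ePTFE −ln(0.138/0.208)/12 = 0.0342. Value read = 2-year value × exp(hazard × *d*).

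| Shared delay (months) | BCA | ePTFE | Difference (points) |
|---|---|---|---|
| 0 | 40.5% | 13.8% | 26.7 |
| 1 | 41.9% | 14.3% | 27.6 |
| 1.5 | 42.6% | 14.5% | 28.1 |
| 3 | 44.8% | 15.3% | 29.5 |
| 6 | 49.5% | 16.9% | 32.6 |

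**4. Effect with varied delays.** A Kaplan-Meier curve extends to the longest-observed patient, so its last value depends on the shortest delays. Simulating 50 per arm with these rates (constant hazard within each year), uniform delays and the last estimate carried forward gives a mean difference of about 27.1 to 27.5 points. A repeat with 20,000 runs per setting and delay ranges from 0.5-1.5 to 1-6 months gave 27.1 to 27.7. The excess over 26.7 is therefore under about 1 point.

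**5. Precision.** With complete 24-month observation the standard error of the difference is √(0.405 × 0.595/50 + 0.138 × 0.862/50) = 0.085, or 8.5 points. In the simulation it is about 8.8 points with delays of 0.5-1.5 months and about 10.8 with delays up to 6 months.

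**6. Numbers at risk at 23 functional months.** A patient must be event-free and have a delay of at most 1 month. The event-free proportion is 0.605 × exp(−0.0334 × 11) = 0.419 for BCA and 0.208 × exp(−0.0342 × 11) = 0.143 for ePTFE.
- Delays uniform on 0.5-1.5 months: half qualify, so 50 × 0.5 × 0.419 = 10.5 BCA and 50 × 0.5 × 0.143 = 3.6 ePTFE patients.
- Delays uniform on 0.5-6 months: 0.5/5.5 = 9.1% qualify, giving about 1.9 and 0.6.
- At 24 months the number is zero in both cases.

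**The case against.** - **The starting point is never stated.** This stands. A reader might infer that no patient can ever be observed to 2 years of functional patency. The documents do not establish that: it follows if the two years run from placement, fails for grafts used early if they run from the second visit, and fails altogether if they run from first use.
- **Hypotheses 2A and 3A may mean status at two years of study follow-up.** The wording allows this. But patency is defined as an interval and Kaplan-Meier is planned, so a 2-year functional rate most naturally means 24 months from first use. If study time was meant, patients would be assessed after unequal functional durations, and the plan should say so.
- **The listed primary outcomes are observable.** This stands. They are not labelled functional, and their base definitions start at placement.
- **Long delays are not shown to be usual.** Monitoring at dialysis follows the day 25-45 visit, which suggests use is generally expected by about 1.5 months. However, the eligibility criteria do not require current dialysis, so longer delays are not excluded.
- **The bias mechanism is assumed.** Nothing says a last estimate would be carried forward and labelled 2-year. Ending follow-up a little early does not by itself bias a Cox hazard ratio. This stands, and it is why bias is not the main harm.

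**Conclusion.** The point holds conditionally. With two years counted from placement, the functional rates in Hypotheses 2A and 3A cannot be directly observed at 24 months from first use, and support just before that point may be very thin. The 2-year placement-based outcomes, the sample size and, at short delays, the 1-year functional results are not affected.

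A reader might take the 29.5- and 32.6-point rows of the table as the likely distortion. They are not: they require every patient to share a 3- or 6-month delay. With varied delays the inflation is under about 1 point, and the larger cost is lost precision and an estimate without observed support at its own time point.

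This rests on the placement reading, on assumed delays, on constant hazards within each year, and on applying the planning rates to the functional clock.

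**What to change.** In 4b, Follow-up, state that the two years run from graft placement, and continue the quarterly contacts until 24 months after first hemodialysis use, or 24 months after placement if the graft is never used, with a stated cap. Record the date of first use. A contact at 27 months after placement covers delays up to 3 months (27 − 24); one at 30 months covers delays up to 6 (30 − 24).

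If contacts cannot be extended, state in Sections 2 and 7 that 2-year patency is reported from placement only. Report functional patency at 1 year and at one later prespecified time within the observed follow-up.

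The first option costs one or two more contacts per patient still followed and a slightly later study end. The second costs only wording, but gives up the 2-year functional comparison in Hypotheses 2A and 3A. This is a cheap improvement.

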Hypothesis 4A: Patients receiving BCA grafts will have lower complication rates at 1 and 2 years follow up than those who receive ePTFE grafts.

Specific Aim 5: To compare re-intervention rates between BCA and ePTFE

Hypothesis 5A: Patients receiving BCA grafts will have a lower re-intervention rate at 1 and 2 years follow up than those who receive ePTFE grafts.

Primary outcomes: Primary, primary assisted and secondary patency rates at 1 and 2 years.

Secondary outcomes: Complication (pseudoaneurysms, infections and steal syndrome) and re-intervention rates at 1 and 2 years.

3. Background

It is known that arteriovenous fistulae (AVF) confer a clear benefit for hemodialysis access in patients with end stage renal disease (ESRD). As a result, national guidelines stipulate AVF as the preferred mode of permanent hemodialysis access¹. In practice, not all patients are good candidates for AVF due to unavailable or inadequate venous conduit(s). In these patients, arteriovenous grafts (AVG) serve as reliable substitutes.

Synthetic grafts such as those made from expanded polytetrafluoroethylene (ePTFE) are the most common AVG's in current use. However, significant drawbacks of ePTFE have been reported in relation to long term patency and infection rates²⁻⁴. These inadequacies inform the need to develop and evaluate biologic conduits that achieve closer mimicry of native human vessels and as result may overcome the disadvantages associated with synthetic grafts.

Since the use of bovine carotid artery (BCA) biological grafts began in the 1970's⁵⁻⁸, significant advances have been made in conduit design and techniques for AVG placement and postoperative endovascular

management. Despite the wide spread use of ePTFE, there is lack of current evidence of a clear advantage of ePTFE over biologic conduits. Prior comparative studies were based on patient cohorts drawn from prior decades^{9,10,11}. This questions the bases for the preference of synthetic conduits in this age. In addition to this lack of current evidence, the more recent study was based on a small cohort of patients¹⁰. Consequently, these inadequately powered studies were unable to establish superiority between AVG options.

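### As worded, primary and assisted primary patency have no end event for a patent graft that is removed, ligated or abandoned for infection, steal, pseudoaneurysm or intolerance

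*Combined protocol and SAP*

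**What the plan says.** Section 2 names three primary outcomes: primary, primary assisted and secondary patency, each at 1 and 2 years. Infection, steal and pseudoaneurysm are counted as complications, which are secondary outcomes.

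Section 4b, under Outcomes, defines the three measures:

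- The first, primary patency, is given as "Interval from graft placement to any intervention for stenosis with or without complete occlusion (thrombosis".
- The second measure, the assisted one, stops at a different event and is given as the "interval from graft placement to the first episode of complete occlusion".
- The third measure, secondary patency, runs until the graft fails, and the plan does not define failure further.

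Functional patency, which Aims 1 to 3 compare, changes only the starting point. It is the "interval from first time graft is used for hemodialysis to qualifying event as above", so it inherits the same end events.

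The same paragraph opens by citing an outside reporting standard: "Outcomes will be assessed and documented per standards for reports dealing with arteriovenous hemodialysis access". It also foresees surgery for other reasons. Its definition of infection includes cases that need surgery, and "surgical intervention will be carried out for patients with stage III or IV steal". Sections 4f and 8a foresee removal of a graft for intolerance or allergic reaction. Section 8a, in its list of risks for patients randomized to the bovine carotid artery (BCA) graft, then takes those patients out of the study.

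Section 7c names Kaplan-Meier and Cox methods. It does not say whether a graft lost for another cause is an event, a competing event or censored.

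**The concern.** Aims 1 and 2 ask which graft stays usable for longer. A graft that is open but has been taken out or tied off is not usable, yet it meets neither end event unless a stenosis intervention or an occlusion came first.

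Three features of the plan make this more than a gap in wording. First, the plan expects complications to differ by material: section 3 says that "significant drawbacks of ePTFE have been reported in relation to long term patency and infection rates", and Hypothesis 4A predicts fewer complications with BCA. Loss for these causes may therefore differ between arms, and censoring it may be informative. Second, the trial is unblinded and the operating surgeon usually handles later interventions (section 4c), so an undefined case would be coded by people who know the graft type. Third, the removal-from-study text in section 8a sits in the BCA risk list, so the patients it drops would come from the experimental arm.

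**Working it through.** **Step 1. Follow one graft through the definitions.** Take a patent graft excised for infection at month 3, with no earlier stenosis intervention or occlusion.

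| Measure | End event in section 4b | Result at month 3 |
|---|---|---|
| Primary | intervention for stenosis | no event |
| Assisted primary | first complete occlusion | no event |
| Secondary | graft failure (undefined) | event, on the natural reading |

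If the graft is carried as patent, its primary and assisted intervals outlast its secondary interval. If it is censored, the estimated curves can still cross. For example, in an arm with no stenosis interventions or occlusions and an assumed 10% removed, primary and assisted patency would be 100% and secondary patency 90%. The order primary ≤ assisted ≤ secondary breaks either way.

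**Step 2. The plan's own sample size.** Section 7c gives 49 per group for a 30-point difference in assisted patency (two-sided alpha 0.05, power 80%). It does not state the pair of rates. Taking 60.5% against 30.5%, with mean rate 0.455:

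- n = [1.96·√(2·0.455·0.545) + 0.842·√(0.605·0.395 + 0.305·0.695)]² / 0.30² = 42.05, so 43.
- With continuity correction: (42.05/4)·[1 + √(1 + 4/(42.05·0.30))]² = 48.5, so 49.

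The stated figure reproduces, and this point does not dispute it.

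**Step 3. Size under assumed loss.** The inputs are the 1-year assisted patency rates in section 7c: 60.5% (BCA) and 20.8% (ePTFE). The documents give no rate of graft removal, so the loss fraction r is an assumption. Suppose the cited rates are occlusion-only, and loss is independent of occlusion and censored. Then patency with loss counted = occlusion-only patency × (1 − r).

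| Assumed loss by 1 year, BCA / ePTFE | BCA | ePTFE | Difference (points) |
|---|---|---|---|
| 0% / 0% | 60.5% | 20.8% | 39.7 |
| 10% / 10% | 0.605 × 0.90 = 54.45% | 0.208 × 0.90 = 18.72% | 35.7 |
| 15% / 5% | 0.605 × 0.85 = 51.4% | 0.208 × 0.95 = 19.8% | 31.7 |
| 5% / 15% | 0.605 × 0.95 = 57.5% | 0.208 × 0.85 = 17.7% | 39.8 |

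The overstatement in an arm is r times that arm's rate, not r itself. At 10% it is 6.05 points for BCA and 2.08 points for ePTFE. Over r = 5% to 20% it runs from 3.0 to 12.1 points (BCA) and from 1.0 to 4.2 points (ePTFE).

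**Step 4. The design pair.** Applying the same factors to 60.5% against 30.5%, with 50 per arm and no continuity correction:

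| Assumed loss, BCA / ePTFE | Difference (points) | Power |
|---|---|---|
| 10% / 10% | 27.0 | 79% |
| 15% / 5% | 22.4 | 63% |
| 5% / 15% | 31.6 | 91% |

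The sign of the change depends on which arm loses more grafts.

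**The case against.** The strongest reply is that the plan is silent rather than wrong. Section 4b invokes a published reporting standard before giving its one-line definitions, and that standard may deal with removal. Secondary patency would pick up these losses, and infection, steal and pseudoaneurysm are reported separately, so the information is not lost from the trial. The plan speaks of surgery for infection and steal, not of removal or closure. Its infection management in section 8a mentions drainage, dressings and antibiotics, and explicit removal appears only for intolerance and allergy. The section 7c complication figures (0.77 ePTFE, 0.34 BCA) point towards the 5%/15% scenario, in which the 1-year difference barely moves (39.8 against 39.7). The cited patency rates may already count removals, in which case step 3 counts them twice.

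Much of this stands as a limit on size. It does not remove the defect. The standard's content is not in the documents, and the plan goes on to state its own definitions. No visible section repairs them; the copy I read shows no text under section 7a, so nothing can be drawn from it either way. Ligation might be read as complete occlusion, but excision of a patent graft much less readily, and that ambiguity itself needs settling.

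A reader might also infer that a graft which thromboses and is abandoned escapes primary patency. On the wording it could, but section 4b refers thrombosed grafts at once for thrombectomy and revision, so this is not the planned course and the point does not rest on it.

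**Conclusion.** The point holds for two of the three primary outcomes. Followed as written, the definitions of primary and assisted primary patency give no end event for a patent graft lost to another cause. Both rates can be overstated, and either can exceed secondary patency.

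A reader might infer more: that such grafts never count as a loss, that every primary outcome is affected, or that the BCA advantage is inflated. The documents do not support these readings. The plan states no rule that such grafts remain patent, a graft with an earlier stenosis intervention or occlusion does count, and secondary patency would naturally capture the loss. Overstatement follows only if these grafts are censored or carried as patent. Bias between arms can go either way: 31.7 to 39.8 points in the scenarios shown, against 39.7.

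Those figures rest on assumed loss rates, on independence, and on reading the cited rates as occlusion-only. They describe censoring. Carrying grafts as patent, or informative loss, would give other values.

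**What to change.** In section 4, Outcomes:

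- End primary patency at the earliest of an intervention to maintain or restore patency, thrombosis, or graft removal, ligation or abandonment for any reason.
- End assisted primary patency at the earliest of first complete occlusion, or graft removal, ligation or abandonment for any reason.
- Define graft failure, for secondary patency, as removal, ligation or abandonment.
- Report the present stenosis-only and occlusion-only definitions as a sensitivity analysis.

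Reconcile section 8a with this, so that a patient whose graft is removed stays in the analysis with the removal counted as an event. At the quarterly contacts in section 4b, record the date and reason of any removal, ligation or abandonment; the plan now speaks only of graft function and outcomes of interest. Settle the wording before outcomes are compared by arm.

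This changes endpoint wording only and no clinical rule. The cost is a paragraph of text, two data items, one added sensitivity analysis and slightly lower absolute patency rates.

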There are over 400,000 patients in the United States who are currently on hemodialysis. An estimated 110,000 new patient annually develop ESRD, requiring dialysis or kidney transplant¹². A conduit that confers better outcomes based on objective evidence will significantly impact the economy and patients' quality of life. In order to address the aforementioned knowledge gaps, we propose a prospective randomized study comparing the functional long-term outcomes between biologic and synthetic AVG conduits in a large cohort of patients. The results of this study will generate evidence needed to inform choice of AVG for permanent hemodialysis access.

4. Study Procedures

a. Study design.

Prospective Randomized Clinical Trial.

Screening

Candidates will be screened for eligibility for the study when evaluated for graft placement as per standard of care. The screening will take place in inpatient or outpatient clinic at either Johns Hopkins Bayview Medical Center or Johns Hopkins Hospital. Physical exam and preoperative vein mapping, if necessary, will be obtained to ensure the unavailability of an autogenous alternative. These surgeries will be elective in nature. Women of child bearing age will be given a urine pregnancy test preoperatively as per standard of care. Those who are pregnant or plan on becoming pregnant for the duration of the study are excluded. Candidates who meet the general inclusion / exclusion criteria will be approached for consent. All HIPAA patient privacy regulations will be observed during discussions with patients.

Consent

Patients will be recruited by the surgery services at Bayview Medical Center or Johns Hopkins Hospital. Patient history and routine preoperative tests will be used to identify comorbidities (such as diabetes, immunosuppression and smoking). Hopkins IRB approved consent designee for this study will meet with the patients prior to the operation to discuss the purpose of the trial and the subject's role, should they choose to participate. The patient will be informed in detail about the study and all their questions will be answered before signing the consent form. The patient will be given ample time to consider the study and

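### The primary patency comparison is given two time origins, first hemodialysis use and graft placement, and a graft lost before first use has no start time on the functional clock

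*Combined protocol and SAP*

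**What the plan says.** Section 2 (Objectives) words the first aim as "Specific Aim 1: To compare functional primary patency between BCA and ePTFE", and Aims 2 and 3 and Hypotheses 2A and 3A likewise use the functional form. The hypothesis attached to Aim 1 drops the word: "Hypothesis 1A: Patients receiving BCA grafts will have a higher primary patency rate at 1 and 2 years follow up". So does the outcome list that closes the section: "Primary outcomes: Primary, primary assisted and secondary patency rates at 1 and 2 years".

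Section 4 (Outcomes) separates the two families. Primary patency is "Interval from graft placement to any intervention for stenosis with or without complete occlusion (thrombosis"). Assisted primary and secondary patency also start at placement. The functional form has its own origin: "Functional patency: interval from first time graft is used for hemodialysis to qualifying event as above". The goal stated under Innovation in section 4 lists functional patency as one more item beside the other three.

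Section 7c names Kaplan-Meier and Cox analyses without a time origin. Section 7d provides for outcome reviews every 6 months and allows stopping on better BCA outcomes. Section 4c says that the trial is not blinded.

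**The concern.** Two things are at stake.

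First, the primary comparison is not fixed to one clock. In an unblinded trial with repeated outcome looks, an analyst could settle on placement or first use after seeing which gives the clearer result.

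Second, the functional clock starts at an event that follows randomisation. A graft that thromboses, fails or is removed before it is ever used for dialysis has no start time, and no visible rule says how it counts. Read literally, it drops out. The comparison is then between used grafts only, and randomisation no longer protects it if the chance of reaching first use depends on the graft material.

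The protocol itself makes early loss relevant. Follow-up note (b) says that most graft abnormalities show by 30 days after surgery, and dialysis-centre monitoring is listed after the visit at postoperative days 25-45: "Thereafter; dialysis center 3 times weekly: The graft will be monitored for its functionality during dialysis sessions". The documents do not say when first use occurs or how many grafts are lost before it.

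**Working it through.** **Which clock each place implies**

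| Place in the protocol | Wording | Origin under section 4 |
|---|---|---|
| Aims 1, 2, 3 | functional | first use |
| Hypothesis 1A | primary, not functional | placement |
| Hypotheses 2A, 3A | functional | first use |
| Primary outcomes line | not functional | placement |
| Section 7c, analysis methods | none given | not stated |

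Aim 1 conflicts with its own hypothesis. Aims 2 and 3 agree with theirs but not with the Primary outcomes line.

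**The plan's own figure.** The sample size for Aims 1-3 is 49 per group. A two-proportion calculation with 60.5% vs 30.5% (the one-year BCA rate less 30 points), two-sided alpha 0.05, 80% power and continuity correction gives 49; without the correction it gives 43. The figure reproduces. It does not settle the clock, because it uses assisted-patency proportions from a prior study whose time origin the protocol does not give.

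**Illustration 1: a difference created.** The early-loss rates are assumptions. Let P be one-year patency from placement and q the proportion lost before first use. Ignoring the later start of the clock, patency among used grafts is P / (1 − q).

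- q = 10%: 0.605 / 0.90 = 0.672
- q = 2%: 0.605 / 0.98 = 0.617
- Gap: 5.5 points, favouring the arm that lost more grafts early, although both arms have the same patency from placement.
- Standard error with 45 and 49 used grafts: √(0.672 × 0.328 / 45 + 0.617 × 0.383 / 49) = 0.099. The gap is 5.5 / 9.9 = 0.56 standard errors.

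Swapping the arms reverses the sign. The range over other assumed rates, with P = 60.5% in both arms:

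| Early loss | Used-graft patency | Gap (points) |
|---|---|---|
| 5% vs 5% | 63.7% vs 63.7% | 0 |
| 5% vs 10% | 63.7% vs 67.2% | 3.5 |
| 2% vs 10% | 61.7% vs 67.2% | 5.5 |
| 5% vs 15% | 63.7% vs 71.2% | 7.5 |
| 5% vs 20% | 63.7% vs 75.6% | 11.9 |

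The standard error is 9.7 to 9.9 points throughout, so only the last row exceeds it.

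The later start changes little. Assume first use at w months and a constant hazard h = −ln(P / (1 − q)) / (12 − w) afterwards; 12-month functional patency is then exp(−12h). For 10% vs 2% loss, first use at day 25 gives 65.3% vs 59.6% (gap 5.7), and at day 45 gives 63.6% vs 57.7% (gap 5.9).

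**Illustration 2: a difference hidden.** Let used-graft patency be 61.7% (0.6173) in both arms, with the same 10% vs 2% loss. Patency from placement is 0.6173 × 0.90 = 0.556 and 0.6173 × 0.98 = 0.605. The functional gap is 0, while 4.9 points are lost from view (standard error 9.9 at 50 per arm).

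**Choosing the clock afterwards.** This was simulated with no true difference: 20,000 trials per setting, 50 per arm, equal loss in month 1, constant hazard afterwards (60.5% patent at 12 months), follow-up to month 24, and a log-rank test on each clock. Each clock alone rejects in about 5% of trials. Reporting whichever is significant rejects in 6.2% (5% loss) or 7.0% (10% loss).

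**The case against.** **This may be a drafting slip.** All three Aims and two of three hypotheses say functional, so Hypothesis 1A and the Primary outcomes line could be shorthand. That is plausible, but nothing visible confirms it. Section 4 defines the terms separately and lists functional patency beside the others. If the functional reading is the intended one, the problem of grafts lost before first use applies in full.

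**The rule may exist where it cannot be seen.** Item 7a, where the primary outcome variable belongs, shows no text in the copy reviewed, and section 4 defers to a reporting standard that is not available here. This stands: one cannot say that the trial has no governing rule, only that the visible text conflicts and shows none. The standard might also say how early losses count.

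**Some wording is weak evidence of intent.** The sizing text does not show that placement was meant, because the source's clock is unknown. The Background phrase "comparing the functional long-term outcomes between biologic and synthetic AVG conduits in a large cohort of patients" need not use the defined term. Neither is relied on.

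**The effect is small.** In the 10% vs 2% example the gaps are about half a standard error, against a planned difference of 30 points. That is fair. The case for change rests on fixing the primary endpoint in advance and keeping the randomised comparison intact, not on these figures.

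**Either clock could be made to work** if it were named and early losses were given a rule. True. Placement is recommended because it starts the clock for every grafted patient.

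**Conclusion.** The point holds for the visible text: the primary patency comparison has two time origins, Aim 1 disagrees with its own hypothesis, and the functional definition as written leaves out grafts lost before first use. This should be resolved before outcomes are compared. Confidence is moderate to high, limited by the unseen item 7a and reporting standard.

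Size and sign cannot be found from the documents. All loss rates above are assumed, and there is no bias if early loss and patency are equal in both arms.

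Three stronger readings are not supported:

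- *That the design favours BCA, or ePTFE.* No early-loss rate is given for either graft.
- *That two-year functional patency cannot be observed.* The protocol says only "The follow up continues up to 2 years to report the final outcomes at end of the study". It states neither when the two years begin nor when grafts are first used.
- *That removing a patent graft after first use never ends primary or assisted patency.* The listed definitions do not mention it, but the cited standard may.

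**What to change.** Align section 2, the Outcomes text in section 4 and the analysis text in section 7 so that they state the following:

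- The primary analysis for Aims 1-3 is patency from graft placement, by randomised arm, keeping every randomised patient who received a graft.
- A graft lost before first use is a failure on the date of loss for all three patency types. A patent graft not yet used is not an event.
- Functional patency is a prespecified supportive analysis, reported with the number of grafts never used in each arm.
- The 6-monthly outcome reviews use the same clock.

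The cost is low. Dates of placement, first use and loss must be recorded, which the two postoperative examinations and the three-monthly contacts can supply. No extra patients or visits are needed. The downside is that functional patency, which the Aims name, becomes supportive, and reported patency may be slightly lower because early losses count.
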